- Overall study success criteria of at least a 30% difference between the test device group and the placebo group, comparing the proportion of individual successes in each group.
- It is anticipated that about 50% of subjects in the test device group and about 20% of subjects in the placebo group will meet the individual success criteria, and
- Intended application of a two-tailed test with an alpha value of 0.05 and Power of 0.8

- the sample size of 25 available subjects per group (test group and the control group, separately) has been determined using the following reference calculator: *Hypothesis Testing: Categorical Data - Estimation of Sample Size and Power for Comparing Two Binomial Proportions* in Bernard Rosner's *Fundamentals of Biostatistics*.

For the purposes of sample size calculation, a subject loss-to-follow-up of 20% is anticipated.

Therefore, a minimum starting sample size of 30 evaluable subjects in each group is needed to ensure that a sufficient number remains at the end of the trial (25 subjects per group) for any significant differences found between groups to be considered statistically valid and representative of the general population being sampled. This results in a total of 60 subjects being enrolled in this study across both study procedure groups.

RANDOMIZATION

Subject allocation to procedure group will be via variable block randomization with varying block sizes of two and four used at random to minimize the likelihood of predicting the next procedure group assignment. In addition, randomization will be stratified by Fitzpatrick Skin Type grouping

Randomization will be attained using computer generation sequence methodology, ensuring that the randomization methodology and the generated allocation sequence is concealed from the investigator and subjects.

Concealment will be insured as follows:

- Each computer-generated randomization sequence is unique and will therefore not be able to be replicated.
- Randomization will occur to either 'Test Group A' or 'B' rather than to a tests or placebo group, and only the study Sponsor will know which assignment corresponds to the active devices and which corresponds to the fake device. The Sponsor will not reveal this information to any source (investigators, subjects, or study Monitor) until the final study data analysis is complete.

TRIPLE BLIND DESIGN

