This clinical study will be a triple-blind design, such that neither the subject, nor the assessor, nor the therapists will be aware of whether a subject is receiving the study procedure with the active (test procedure group assignment) or the 'fake' (placebo procedure group assignment) Multi Radiance Medical MR5 Prototype Device until after the study is completed.

Maintenance of study triple-blind throughout the entire course of the study will be achieved through the following means:

- Each subject will be randomly assigned to 'Test Group A' or 'B' by the independent study Monitor. Only the study Sponsor will know which label 'Test Group A' or 'B' corresponds to the actual (test) MR5 device and which label corresponds to the 'fake' device until the final study data analysis is complete. The Sponsor will ensure that this information is stored and maintained confidentially at the Sponsor's work site. This knowledge will not be shared with the investigators, the subjects, or the study Monitor until the final data analysis is complete.
- The fake (placebo) MR5 device is designed to have the same physical appearance as the actual MR5 device, including the appearance of any **visible** light output. Therefore, both the test and sham devices emit light when activated that is indistinguishable to both

the subject and to the investigator. As the laser light does not put out any notable degree of heat or noise, these are not distinguishing factors for subjects between the four groups.

3) There will be two independent investigators interacting with subjects at each test site:

- Administration investigator*: who will be responsible for administrating the study procedures; and
- Assessment investigator*: who will be responsible for recording the study outcome measures

Only the administration investigator will be aware of whether a subject is assigned to 'Test Group A' or 'B', although he or she will not be made aware of whether 'Test Group A' or 'B' corresponds to the true or fake laser. Neither the assessment investigator nor the subject will be aware of the subject's A/B Group assignment. In this way, the assessment investigator will not be able to form an association between A/B Procedure Group and active/sham device over the course of the study if a treatment effect is observed.

4) During the MR5 procedures, both the subject and the administration investigator will wear Laser Safety Industries protective eyewear that filter out the laser light spectrum.

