- Each of the six procedure administration visits will occur within the same on-hour timeframe, as explained above under 'ESTABLISHMENT OF PROCEDURE ADMINISTRATION VISIT SCHEDULE' above.
- Each procedure administration lasts 20 minutes.
- The procedure administrations with the MR5® Laser is administered by the procedure administrator at the test site.
- Prior to administration of treatment protocol skin should be cleansed and verify there is no broken skin.

The study procedure administration protocol is as follows:

1. The subject enters the procedure administration room and is situated in a seated position.
2. The skin should be prepared for treatment by cleansing skin and verification of no broken skin.
3. The subject is correctly fitted with the safety glasses.
4. The procedure administrator puts on the safety glasses and selects the Multi Radiance Medical® MR5® Prototype Device A or B according to the subject's procedure group randomization.
5. The Prototype Device emitter is statically held by direct contact with the skin on each of the target areas:
Identified in diagram (over the Lateral Epicondyle) for the light administration phase for 60s each location.
6. The total procedure administration duration is 5 minutes for the laser portion of the treatment.

Laser

	1 SPL	IR	Red	Total
Photons/sec	5.69E+15	1.10E+18	6.75E+17	1.78E+18
Time, sec	Irrad, W/cm2	0.002841	0.0625	0.05 1.15E-01
60 Energy, J		0.075	15	12 2.71E+01
Fluence, J/cm2	0.170455		3.75	3 6.92E+00

PROCEDURE ADMINISTRATION PHASE MEASURES

Daily throughout the three-week procedure administration phase, the subject will continue at home to:

- maintain application of his or her individualized pain management regimen, as during the two-week stabilization phase, and
- complete the Subject Daily Diary, as applicable

WITHIN 24 HOURS OF COMPLETION OF THE FINAL (6TH) PROCEDURE ADMINISTRATION

- Degree of Pain Rating. The exact time the VAS rating is recorded will be noted.
- PRTEE, Grip Strength and TNFa measurements will be noted.
- Subject Satisfaction with Overall Outcome Rating
- Perceived Group Assignment
- Investigator Adverse Events Evaluation

POST-PROCEDURE ADMINISTRATION PHASE

The post-procedure administration phase encompasses the one-week period immediately following completion of the procedure administration phase and comprises the following evaluation points and associated measures.

POST-PROCEDURE ADMINISTRATION PHASE EVALUATION POINTS AND MEASURES

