- b. **Parametric ANCOVA model** analysis with the mean change from baseline to study endpoint in Lateral Epicondyle pain ratings on the VAS as the dependent variable, procedure group as the independent variable of interest and average dosage/frequency of use any component of the individualized pain management regimen. A two-tailed significance level of 5% will be considered to be statistically significant.
- c. **T-test analysis** to compare the frequency of usage of the pain management regimen across study duration between treatment groups.

- d. **Linear regression analysis** to evaluate the impact of frequency of usage of the pain management regimen across study duration on the primary outcome measure between procedure groups
- e. **Log Rank statistics** to evaluate differences in the time to first use of the pain management regimen between test and placebo procedure groups

BLINDING EFFICACY EVALUATION

Statistical evaluation of blinding efficacy will be performed as follows:

- (i) The percentage of subjects who correctly perceived their procedure group assignment and the percentage of subjects who did not correctly perceive their procedure group assignment will be calculated.
- (ii) The percentage of times the administration investigators correctly perceived subjects' procedure group assignment and the percentage of times the assessment investigators did not correctly perceive subjects' procedure group assignment will be calculated.
- (iii) The percentage of times the assessment investigators correctly perceived subjects' procedure group assignment and the percentage of times the assessment investigators did not correctly perceive subjects' procedure group assignment will be calculated.
- (iv) The **Fischer's Exact categorical analysis technique** for comparison of proportion of successes (accurate procedure group assignment determination) and failures (inaccurate procedure group assignment determination) between subject groups will be performed for each of the subject, administration investigator and assessment investigator determinations.
 - Comparisons will be made to evaluate if the proportion of correctly guessed subject procedure group assignments is greater than the proportion of incorrectly guessed subject group assignments.
 - Comparison will be made for each of the groups of subjects, administration investigators and assessment investigators, within and between treatment groups.

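### The treating investigator sees every subject's A/B letter, so that person's guesses cluster by site, and the planned per-subject tests of them can miss full unblinding or signal it by chance

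*Combined protocol and SAP*

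**What the plan says.** The RANDOMIZATION section sets up a two-letter code: "Randomization will occur to either 'Test Group A' or 'B' rather than to a tests or placebo group". TRIPLE BLIND DESIGN adds: "Only the study Sponsor will know which label 'Test Group A' or 'B' corresponds to the actual (test) MR5 device". No subject-specific or site-specific code is described.

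Item 3 of the same section provides for one treating and one assessing role: "There will be two independent investigators interacting with subjects at each test site". Of the two, "Only the administration investigator will be aware of whether a subject is assigned to" Group A or B. The step list under PROCEDURE ADMINISTRATION PROTOCOL has this person select the "Prototype Device A or B according to the subject"'s allocation, and each subject has six sessions. The other parties are kept from the letter: "Neither the assessment investigator nor the subject will be aware of the subject"'s A/B assignment. The stated purpose is that "the assessment investigator will not be able to form an association between A/B Procedure Group and active/sham device".

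PERCEIVED GROUP ASSIGNMENT asks the subject and both investigators, separately and for each subject, which device they think was used and why. BLINDING EFFICACY EVALUATION, item (iv), then plans Fisher's exact test comparing accurate and inaccurate determinations between the subject groups, "for each of the subject, administration investigator and assessment investigator determinations". Its sub-bullets add a comparison of whether correct guesses outnumber incorrect ones, for each type of guesser.

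**The concern.** The plan recognises that someone who sees the letters could link a letter to the active device, and it protects the assessor against this. The administration investigator is left exposed to the same hazard, although the design counts the therapists as blinded. Once this person settles on a letter, the guess for every other subject at the site follows from it. The guesses then carry about as much information as there are investigators.

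The blinding section makes no stated allowance for this. It treats the administration investigator's guesses in the same way as those of subjects, who are separate people and do not know their letter. At stake is whether the blinding report for this role means anything. The primary outcome is a self-rated VAS, and this investigator meets the subject repeatedly. A belief about the code could reach the rating through that contact, so the blinding of this role deserves an interpretable check.

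**Working it through.** The plan gives no figure here to reproduce. The check is an exact enumeration.

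**Inputs**
- Site sizes, summed from the tables in the Sample stratification distribution plan. Site 1: test 7 + 5 = 12, placebo 8 + 4 = 12, total 24. Site 2: 7 and 7, total 14. Site 3: 6 and 6, total 12. All sites: 25 per group, 50 subjects.
- Assumed: one administration investigator per site, each with no real knowledge, who picks a letter by coin flip and applies it to every subject at the site.
- Assumed: one-sided alpha of 0.05 for the correct-versus-incorrect comparison. The blinding section states no alpha and names no test for that comparison.

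**Eight equally likely patterns (2^3 = 8)**

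Fisher p compares accuracy between the groups. Binomial p is P(X ≥ c) for X ~ Bin(50, 0.5), where c is the number correct.

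| Sites that guess right | Correct of 50 | Correct by group (of 25) | Fisher p | Binomial p, one-sided |
|---|---|---|---|---|
| none | 0 | 0 v 0 | 1.0 | 1.0 |
| 3 | 12 | 6 v 6 | 1.0 | 0.99996 |
| 2 | 14 | 7 v 7 | 1.0 | 0.9995 |
| 1 | 24 | 12 v 12 | 1.0 | 0.66 |
| 2 and 3 | 26 | 13 v 13 | 1.0 | 0.44 |
| 1 and 3 | 36 | 18 v 18 | 1.0 | 0.0013 |
| 1 and 2 | 38 | 19 v 19 | 1.0 | 0.00015 |
| all | 50 | 25 v 25 | 1.0 | 0.5^50, below 10^-15 |

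**Fisher's test as worded.** A consistent guesser is right, or wrong, for both groups at once. The sites are balanced, so the two groups always have the same number correct. The observed table is then the most probable one for its margins (or the only one, with 0 or 50 correct), and p = 1.0. The 50-of-50 result would give p = 1.0 for any type of guesser. What is particular to this role is that seeing the letter makes all-right or all-wrong site patterns the natural outcome.

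**Correct versus incorrect.** Three of the eight patterns (36, 38 and 50 correct) fall below 0.05: 3/8 = 37.5%. With 50 independent coin-flip guesses, the same test rejects in 3.2%.

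**Partial consistency.** Suppose the investigator follows the belief for a fraction q of subjects and guesses at random for the rest (4,000 simulated trials per value).

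| q | Shows more correct than incorrect |
|---|---|
| 0.25 | 11.2% |
| 0.50 | 22.5% |
| 0.75 | 34.1% |

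**If the investigator is the unit.** Three independent guesses are all right by luck with probability 0.5^3 = 0.125. With three units, no 5% test is possible.

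**The case against.** The strongest reply is that this is an ancillary diagnostic. No success criterion depends on it, and guesses are asked subject by subject with reasons, so an investigator may well vary them. The first part stands and limits the importance of the point. The second is why the range for partial consistency is given: clustering still inflates the error rate at q = 0.25.

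Some stronger readings are tempting, and the documents do not support them.
- *One correct guess unblinds the whole trial.* The letter is withheld from subjects and assessors. A decoded letter exposes, to that investigator, the subjects he or she treats. It reaches other sites only if it is shared, and only if the code is common to all sites. A common code is the plain reading, though site-specific codes are not expressly excluded. A guess is also not knowledge.
- *The Fisher test raises false alarms.* As worded it does the opposite under consistent guessing, because it never rejects. The 37.5% belongs to the separate correct-versus-incorrect comparison.
- *Guesses would depart from chance in either direction 75% of the time.* Six of the eight patterns do so in a two-sided test, but the plan does not clearly specify such a test for these guesses.
- *The plan would declare blinding failed.* The only explicit failure rule, item (v), is qualitative and turns on comments about sensory clues or a compromised blind. Guesses explained by treatment response count in favour of blinding.

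The blinding section also says that its numerical assessment follows a cited methods paper. The documents do not reproduce that method, so it can be credited with neither curing nor sharing the problem.

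**Conclusion.** The planned per-subject analysis of the administration investigator's guesses is unsound as written. The Fisher comparison gives p = 1.0 whenever each investigator is consistent, including at 50 of 50 correct, and so cannot reveal complete unblinding of this role. The correct-versus-incorrect comparison would show an excess of correct guesses by chance in 37.5% of cases under full consistency, and in about 11% to 34% if the belief is followed for 25% to 75% of subjects.

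These figures rest on one administration investigator per site, independent beliefs between sites, the planned site sizes of 24, 14 and 12 with equal groups, and a one-sided 0.05 that the plan does not state. The exact percentages would move with these assumptions, but the clustering would not disappear. The point does not touch the primary efficacy analysis, the sample size or the subjects' own guesses. It is a worthwhile correction of minor weight.

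**What to change.** In BLINDING EFFICACY EVALUATION, item (iv), drop both per-subject comparisons for the administration investigator: Fisher's test and correct versus incorrect. Report instead, descriptively, this person's guess once per site and letter, with the stated reasons already collected for item (v). Keep the planned tests for subjects. This costs SAP wording only.

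Optionally, use a different letter pair at each site and randomize by site which letter is active, so that a decoded letter does not carry over to other sites. This does not cure clustering within a site, so it supplements the change of analysis and does not replace it. Its cost is relabelling, three keys held by the sponsor instead of one, and a site-level recode before blinded analysis. The documents give no device inventory, so whether further devices would be needed cannot be judged from them.

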The informed consent form that will be used in this clinical study is contained in **Appendix D**.

ASSIGNMENT OF SUBJECT IDENTIFICATION NUMBER

The subject will be assigned a unique subject identification number based upon his or her order of entry into the study.

Additional information about the informed consent and subject ID number assignment is contained in a later section of the protocol titled, "SAFETY AND CONFIDENTIALITY ISSUES."

STUDY QUALIFICATION EVALUATION: INCLUSIONS/EXCLUSION CRITERION

INCLUSION CRITERIA

To be eligible for study participation, a subject must satisfy each of the following criteria.

Patient history: History of one or more the following:

- Patients with a history of pain around the Lateral Epicondyle for at least 1 month;
- Tenderness localized to the epicondyle and anterodistal region of the epicondyle with palpation;

- 2 of 4 positive results of provocative tests comprising of Maudsley's, Cozen's, Thomsen and Mill's tests (Whaley, Baker 2004);
- Aged between 18 and 50 years;
- Both genders.

Reference - Whaley AL, Baker CL. *Lateral epicondylitis. Clin Sports Med.* 2004; 23(4):677-691

Medication Use History: Where applicable, history of attaining relief from Lateral Epicondyle pain from taking over-the-counter and/or prescription muscle relaxants; nonsteroidal anti-inflammatories (NSAIDs) such as ibuprofen or naproxen, and acetaminophen.

Previous Records Review (x-rays, MRI, CT scans, etc.): where pre-existing and available, previous records review that indicates muscle or ligament injury and the absence of Degenerative Joint Disorder (DJD)

Physical Examination of the Lateral Epicondyle Region.

- Painful range of motion
- Pain and weakness upon grip strength and wrist extension
- Muscles in Lateral Epicondyle feel hard, tight or knotted upon palpation
- Muscles in Lateral Epicondyle feel hard, tight or knotted upon palpation
- Lateral Epicondyle pain is persisting over one month
- Self-reported Degree of Pain rating on the 0-100 VAS pain scale for the Lateral Epicondyle region is 50 or greater

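### The patient-history inclusion criterion asks for only one of five items, one of which everyone meets, so localized tenderness and the provocative tests are optional as written

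*Combined protocol and SAP*

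**What the plan says.** The Inclusion Criteria section opens with a general rule: "To be eligible for study participation, a subject must satisfy each of the following criteria". The first criterion, on patient history, then sets its own, looser rule: "History of one or more the following". Five items follow:

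- a pain history of one month or longer at the lateral epicondyle
- tenderness on palpation, confined to the epicondyle and the area just in front of and below it
- a rule on clinical tests, worded "2 of 4 positive results of provocative tests comprising of Maudsley's, Cozen's, Thomsen and Mill's tests"
- an age range, worded "Aged between 18 and 50 years"
- a statement that men and women may both enter

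A separate list, headed as the physical examination of the lateral epicondyle region, carries no one-or-more wording. It asks for painful range of motion, pain with weakness on grip and wrist extension, hard or knotted muscles on palpation, pain lasting over a month, and a VAS rating of at least 50. It also contains an age criterion of 18 or above, with no upper limit, and a second statement that either sex may enter.

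Under Study Indication, the Diagnosis paragraph says that tenderness over the extensor carpi radialis brevis or the common extensor origin is what substantiates the diagnosis.

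**The concern.** The two findings that most directly identify the condition are alternatives in a list that can be satisfied without either of them. A site that follows the text literally may enrol a subject who has neither localized tenderness nor 2 of 4 positive tests. A site that reads the lead-in as covering every bullet would refuse the same subject. With three sites, eligibility could be applied differently from one to another.

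The indication sought is specific to pain from lateral epicondylitis, and the results are meant to support a De Novo submission. If the criteria do not require the diagnosis to be established, the link between the trial population and the claim is weaker. Any subjects whose pain has another cause may also dilute the treatment difference. The same wording makes the 18-to-50 age range optional.

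**Working it through.** No figure in the plan needs to be reproduced here. The check is a logical one: which candidates does the criterion as written turn away?

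**Step 1: the criterion alone.** Call the five items P (pain for at least a month), T (tenderness), V (2 of 4 tests), A (age 18 to 50) and G (gender). G is met by everyone, so there are 2 × 2 × 2 × 2 = 16 possible patterns on P, T, V and A. The rule is P + T + V + A + G ≥ 1. Since G = 1 always, 16 of 16 pass. In 2 × 2 = 4 of these, both T and V are absent.

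**Step 2: add what is required elsewhere.** Pain duration is mandatory through the physical-examination list, and pain of less than one month is an exclusion. Fixing P = 1 leaves 2 × 2 × 2 = 8 patterns. All 8 pass, and 2 of the 8 have neither T nor V. If all five items were required, 1 of the 8 would pass.

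**Step 3: suppose age and gender are in the list by mistake.** Take only P, T and V. With P = 1 there are 2 × 2 = 4 patterns. All 4 still pass the one-or-more rule, because pain duration alone satisfies it, and 1 of the 4 has neither T nor V. The problem therefore does not depend on the odd placement of age and gender.

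These are counts of logical patterns, not proportions of patients. They show that the criterion removes nobody; they do not show how many subjects would lack the findings.

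**Step 4: look for T and V elsewhere in the eligibility text.**

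| Item | Required elsewhere? |
|---|---|
| Pain for at least a month | Yes: physical-examination list and exclusion |
| Localized tenderness | No: the palpation bullet concerns muscle texture, not tenderness at the epicondyle |
| 2 of 4 provocative tests | No: pain and weakness on grip and wrist extension is related, but is not this rule |
| Age 18 to 50 | No: the separate age criterion has no upper limit |
| Gender | Restated, and excludes nobody |

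**The case against.** The strongest reply is that this is a drafting slip. Age and gender cannot be items of history, and the lead-in requires every criterion to be met, so an experienced investigator would take all the bullets as mandatory. That may well be the intention. But one-or-more is the more specific instruction for this list, and a subject who meets one item has satisfied that criterion. At best the two sentences contradict each other. The case report forms (Appendix E) are not in the text reviewed, so they cannot settle how sites check each item.

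A second reply is that other safeguards remain, and this one stands.

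- The examination items are mandatory. Pain and weakness on resisted wrist extension and weak grip are among the protocol's own objective findings for this condition.
- The exclusions name radial tunnel syndrome, cervical radiculopathy, peripheral nerve disease, fibromyalgia and others. Absence of degenerative joint disorder is asked for where records exist.
- Recruitment is among people treated for, seeking treatment for, or answering advertisements about lateral epicondylitis, and qualification is by a licensed provider experienced in treating it.

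The cover is not complete. Medial epicondylitis, cervical disc disease and cervical spondylosis are on the protocol's differential list but are not named as exclusions, and the exclusion for secondary orthopedic problems is undefined.

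Two stronger readings are tempting, and neither is supported. A reader might infer that someone could enter on gender alone, or with no elbow-specific finding. The remaining mandatory items rule that out.

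A reader might also infer that misdiagnosed subjects would push the expected difference below the plan's 30-point success criterion. If a share f of subjects lacked the condition and gained nothing beyond placebo, the difference would be 30 × (1 − f): 27 points at an assumed 10%, 24 at an assumed 20%. But the documents give no value for f, and the protocol describes a general pain-relief mechanism, so a zero effect in such subjects is a further assumption. The anticipated difference (50% against 20%) equals the criterion exactly, so any f above zero falls below it. That comparison reflects where the criterion was set and says little about eligibility.

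**Conclusion.** The point holds as a defect in an operative eligibility rule. As written, the patient-history criterion excludes nobody, contradicts or at least strains against its lead-in, and leaves localized tenderness and the 2-of-4 test rule optional. This conclusion rests only on the wording and on the absence of those two items as requirements elsewhere in the inclusion and exclusion lists.

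The consequence is limited. Partial screening remains, and random allocation means that any subjects without the condition would be expected in both groups, so the issue is dilution and a less secure diagnosis-specific claim rather than a biased comparison. The amount of dilution cannot be estimated from the documents. The text should be corrected because the change is small and an eligibility rule must give the same answer at all three sites.

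**What to change.** Reword the patient-history criterion so that it agrees with the lead-in: pain duration, localized tenderness and 2 of 4 positive provocative tests are all required. Take age and gender out of that list and state each once as a separate criterion. Reconcile the 18-to-50 range with the separate criterion of 18 or above; the sponsor must decide which is intended. Check that the screening form in Appendix E records tenderness and the result of each of the four tests, so that eligibility can be verified.

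The cost is a short protocol edit and any matching change to the screening form. No new assessment is added, since tenderness and the tests are already listed. The downside is that a few more candidates may fail screening.
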